## **GENERAL INFORMATION**

Acronym: PROMIS

**Title:** Evaluation of Multi-Parametric Magnetic Resonance Imaging in the Diagnosis and Characterisation of Prostate Cancer

This document describes a Health Technology Assessment (HTA) funded study called PROMIS which is being sponsored by University College London (UCL). PROMIS is being conducted by UCL and the Medical Research Council Clinical Trials Unit (MRC CTU). This document is a protocol that provides information about procedures for entering patients into PROMIS. This protocol should not be used as an aide-memoire or guide for the treatment of other patients. Amendments may be necessary; these will be circulated to known collaborating investigators, but centres entering patients for the first time are advised to contact the MRC CTU, Cancer Group, London to confirm they have the most up to date version of the protocol.

If in doubt as to the procedure for registering patients or for other study queries, please contact the Trial Manager at the MRC CTU. For urgent clinical problems relating to this study, please contact the Chief Investigator, [name].

This study will comply with the principles of Good Clinical Practice (GCP) as laid down by Commission Directive 2005/28/EC and by Statutory Instrument 2004/1031 [Amendments; 2006 No. 1928]. It will be conducted in compliance with the protocol, MRC GCP, the Data Protection Act (DPA no. Z5886415) and any other appropriate requirements.

## **APPENDICES**

Please refer to PROMIS Protocol Appendices

## ABBREVIATIONS AND GLOSSARY

ADC	Apparent diffusion coefficient
AE	Adverse event
CI	Confidence interval
СРВ	Combined prostate biopsy
CRF	Case report form
СТА	Clinical Trials Authorisation
DCE	Dynamic Contrast Enhanced
DRE	Digital rectal examination
DW	Diffusion weighting
Gd-DTPA	Gadolinium-diethylenetriamine pentaacetic acid
HE	Health economics
HES	Hospital Episode Statistics
HRQL	Health-related quality of life
HTA	Health Technology Assessment
MRC	Medical Research Council
CTU	Clinical Trials Unit
MP-MRI	Multi-Parametric Magnetic Resonance Imaging
MRI	Magnetic Resonance Imaging
NCRN	National Cancer Research Network
NHS	National Health Service
NICE	National Institute for Health and Clinical Excellence
NIHR	National Institute for Health Research
NPV	Negative predictive value
PI	Principal Investigator
PIS	Patient information sheet
PPV	Positive predictive value
PROMIS	Prostate MRI Imaging Study
PSA	Prostate specific antigen
QA	Quality assurance
QALY	Quality adjusted life years
QC	Quality control
QoL	Quality of life
ROI	Region of interest
RP	Radical prostatectomy
SAE	Serious adverse event
SOP	Standard Operating Procedures
STARD	STAndards for the Reporting of Diagnostic accuracy studies
TMG	Trial Management Group
ТРМ	Template prostate mapping
TRUS	Transrectal ultrasound
TSC	Trial Steering Committee
UCL	University College London
UCLH	University College London Hospital

### 1. SUMMARY

#### 1.1 Abstract and summary

The purpose of PROMIS (MRC PR11) is to trial the use of multi-parametric Magnetic Resonance Imaging (MP-MRI) as a tool in the diagnosis of prostate cancer. In particular, PROMIS aims to evaluate whether MP-MRI improves the ability to detect as well as rule-out clinically significant prostate cancer in a group of men currently advised to have prostate biopsy.

At present, men with raised serum prostate specific antigen (PSA) are advised to have a transrectal ultrasound (TRUS) guided biopsy. This study will investigate whether imaging prior to biopsy can be incorporated into the existing diagnostic pathway for prostate cancer. We will evaluate whether men with a raised PSA, or other risk factors for harbouring prostate cancer, should first undergo a MP-MRI in order to select a group that could safely forego prostate biopsy. In addition, this study will evaluate the ability of MP-MRI to identify lesions for selective biopsy.

In order to evaluate the diagnostic accuracy of MP-MRI (index test) against the TRUS guided biopsy (current standard test) both procedures need to be compared to a reference standard. This reference standard needs to be accurate at both detecting and ruling-out prostate cancer and amenable to application to all men at risk. Template Prostate Mapping (TPM) meets the necessary performance characteristics of such a reference test. It is performed under a general/spinal anaesthetic.

By design, PROMIS, conforms to a validating paired cohort study (see Oxford Centre for Evidence-based Medicine, 'Levels of Evidence', 1b, http://www.cebm.net/index.aspx?o=1025). All men in the study will have a MP-MRI (index test), followed by both a TPM biopsy (reference test) and a standard TRUS guided biopsy (current standard test). These 3 tests will be assessed and reported independently from each other.

[figure not shown]
The study is divided into a pilot and a main phase. The pilot will be run in two centres, University College London Hospitals NHS Foundation Trust and North Hampshire Hospitals NHS Trust and aims to recruit 50 patients over one year. The pilot will assess recruitment and the safety of administering the tests, particularly the combined prostate biopsy (CPB) procedure of TPM and TRUS under general/spinal anaesthesia. Continuation to the main phase will depend on an independent review of the data.

The main phase will be extended to approximately 6 centres in total (including the 2 pilot centres), recruiting up to 714 men to have all 3 tests over an additional 2 to 3 years.

The main objectives of the trial are:

- To assess the ability of MP-MRI to identify men who can safely avoid unnecessary biopsy.
- To assess the ability of the MP-MRI based pathway to improve the rate of detection of clinically significant cancer as compared to TRUS biopsy.
- To estimate the cost-effectiveness of an MP-MRI based diagnostic pathway. Using data from the main study and the wider literature, the study will consider the implications of alternative diagnostic strategies for NHS cost and men's quality-adjusted survival duration.

#### 1.2 Trial schema

# Primary Outcomes Pilot Phase 1. Safety 2. Recruitment Main Trial 1. Proportion of men who could safely avoid biopsy as determined by specificity and negative predictive values 2. Proportion of men correctly identified by MP-MRI to have clinically significant prostate cancer as determined by sensitivity and positive predictive values

## 2. INTRODUCTION & BACKGROUND

#### 2.1 General overview and rationale

There are approximately 35,000 new cases of prostate cancer annually in the UK. The incidence has doubled in the last 15 years, mainly due to increased use of serum Prostate Specific Antigen (PSA) testing in healthy men. As a result, prostate cancer has become the most common cancer in men. The existing diagnostic pathway will, if left unchecked, result in a further rise in incidence and associated costs to the NHS without necessarily reducing the risk of dying from the disease. Many, if not most, prostate cancers that are currently detected are clinically insignificant. Therefore, over-diagnosis, the detection of a cancer that would not have had any clinical impact on the individual during his remaining life, is a major problem.

This assertion has received considerable support from two large randomised controlled trials of prostate cancer screening. While the US screening trial showed no evidence of a survival benefit, the European Screening study showed a modest reduction in risk of death from prostate cancer in those screened. The number needed to screen was 1410 and the number needed to treat 48 to extend the life of one man over a ten year period. Commentators were quick to voice their concern that over-diagnosis, and hence over-treatment and associated morbidity, would increase further if PSA screening were adopted more widely. However, if a diagnostic method was available that was more specific for *clinically significant* prostate cancer, the beneficial effect of screening on mortality could be retained, while minimising over-diagnosis and over-treatment.

#### 2.2 Diagnostic pathway

At present, a man is judged to be at risk of harbouring prostate cancer if he has any of the following: a raised serum PSA level (the majority), an abnormal digital rectal examination (DRE), a positive family history or a specific ethnic risk profile. Such men are currently advised to have a transrectal ultrasound (TRUS) guided prostate biopsy. Between 59,000 and 80,000 men have a TRUS biopsy in the UK each year. Men undergo prostate biopsy in the absence of accurate imaging that can visualise a suspicious lesion. Ultrasound is used to identify the prostate, not the suspect lesion. The result is that biopsies are taken 'blindly' from areas of the gland. This approach (Figure 1, current diagnostic pathway) contrasts markedly with that used for other cancers. The typical approach is either to see (e.g. at endoscopy) or to image (e.g. using mammography) a suspect lesion, and then to biopsy it directly.

[figure not shown]
In PROMIS, we will determine whether it is appropriate that men with a risk factor for harbouring clinically significant cancer should first undergo MP-MRI to select who should, or should not, have a prostate biopsy. MP-MRI would therefore act as a triage test (Figure 1, proposed diagnostic pathway). This could offer several important advantages:

- Less over-diagnosis, i.e. fewer *clinically insignificant* prostate cancers detected by avoiding unnecessary biopsy of men who do not have clinically significant cancer.
- Less over-treatment as fewer *clinically insignificant* prostate cancers are detected.
- Increased detection of *clinically significant* prostate cancers by directing biopsies to areas of the prostate that appear abnormal on MP-MRI.
- Improved characterisation of individual cancers due to more representative biopsy sampling.

• Reduced complications (sepsis and bleeding) as fewer men biopsied and fewer biopsies taken in men that are biopsied.

The overall result also has the potential to offer a more cost-effective use of NHS resources. This area of research has been designated as important both by the UK's National Institute for Health and Clinical Excellence (Prostate Cancer Management Guidelines, 2009) and the US National Institute of Health - National Cancer Institute.

#### Figure 1: Current and proposed diagnostic pathway for prostate cancer

Proposed new diagnostic pathway

Please note: this is a proposed future diagnostic pathway and NOT the pathway patients will take in PROMIS (See Trial Schema 1.2)

#### 2.3 Prostate biopsy

Current diagnostic pathway

#### 2.3.1 Over-detection of insignificant prostate cancer

Middle-aged men in the general population who undergo TRUS biopsy have a 25% chance of being diagnosed with prostate cancer. This compares with a lifetime risk of 6-8% for symptomatic prostate cancer, and illustrates the over-diagnosis of harmless cancers in many men who undergo TRUS biopsies (Figure 2).

[figure not shown]
#### Figure 2: Over-detection of insignificant prostate cancer

#### 2.3.2 Under-detection of clinically significant prostate cancer

TRUS biopsies have an estimated false negative rate of 30%-45%. The clinician takes 10-12 biopsies in a manner that attempts to obtain representative tissue within the peripheral zone (Figure 3a). However, several parts of the gland are not well sampled using this approach (systematic error). The anterior part of the gland may be missed as a result of its greater distance from the rectum (Figure 3b, 3c). Tissue in the midline is missed due to efforts to avoid the urethra, while the apex of the prostate is often inaccessible by the transrectal route.

[figure not shown]
#### Figure 3: Under-detection of clinically significant prostate cancer

#### 2.3.3 Inaccurate risk stratification

TRUS biopsies can be unrepresentative of the true burden of cancer due to random sampling error (Figure 4). Either the size or the grade of cancer may be underestimated if the cancer tissue obtained on TRUS biopsy is not representative. Figure 4 illustrates how accurate estimation of tumour size will depend on hitting the centre of a lesion. At present, because these lesions are not visualised, this relies purely on chance. However, improved risk stratification is likely if MRI results can be used to guide TRUS biopsies.

#### Figure 4: Inaccurate risk stratification

The pathological status derived from TRUS biopsies can be unreliable if the test is reapplied, not only at discriminating clinically important cancer from clinically unimportant prostate cancer but also at attributing a non cancer status from a cancer status in about a quarter of men subject to serial testing.

#### 2.3.4 Side effects

TRUS biopsy is associated with a number of complications, the most important being urinary tract infection (1-8%) that can result in life-threatening sepsis (1-4%). Haematuria (50%), haematospermia (30%), pain/discomfort (most), dysuria (most) and urinary retention (1%) can also be expected.

#### 2.4 MRI

#### 2.4.1 Diagnostic accuracy of MRI in prostate cancer

The evidence base suggests that MRI can achieve both a sensitivity and specificity between 70-90% for the detection of clinically significant prostate cancer. However, a systematic review of the literature, found the quality of the initial studies evaluating MRI to be disappointing (see section 2.4.3). They repeatedly showed low sensitivity and specificity as well as high inter-observer variability, even when using high resolution endorectal MRI. Since these early reports, much has changed including an appreciation of the impact of post-biopsy changes on MRI, technological improvements such as increasing magnetic field strength (from 0.5 Tesla to 1.5 Tesla and 3.0 Tesla), shorter pulse sequences enabling faster image acquisition, and the introduction of functional imaging in the form of diffusion weighting (DW) and dynamic contrast-enhancement (DCE).

The main types of MR images available are those produced by T2 weighting (T2), diffusion weighting (DW) and dynamic contrast enhancement (DCE). Each MR parameter in isolation has been reported to have the range of sensitivity and specificity shown in Table 1. For more information of the main types of MR images please see Appendix I: Main types of MR images.

#### 2.4.2 MP-MRI

Multi-parametric approaches (combining these 3 sequences together) have also been investigated. Although small, single centre case series have found an advantage for using two or three MR sequences rather than just one. None have evaluated the clinical validity of MP-MRI in the population of interest against an accurate and appropriate reference standard within a multi-centre study.

ensitivity and specificity of Mixt parameters as reported in the interature					
Parameter	Number (mean)	Sensitivity	Specificity		
T2	12-320 (97)	37-96%	21-67%		
DW	11-95 (42)	57-90%	79-88%		
DCE	23-54 (41)	71-87%	61-89%		

Table 1: Sensitivity and	specificity of MRI	parameters as re	ported in the literature

#### 2.4.3 MRI literature limitations

There are important limitations with previous studies investigating the diagnostic accuracy of MRI for prostate cancer:

- **Biopsy artefact**: studies mostly evaluate MRI after biopsy. However the biopsy procedure can affect what is seen on the MRI which can result in an increase in false positive or negative results.
- Limited application: studies mostly evaluate only the peripheral zone of the prostate, ignoring up to one third of prostate cancers.
- **Segmentation**: when each region of interest (ROI) is segmented to achieve sufficient datasets, increasing the power of the analysis and accuracy by incorrectly treating each ROI as independent.
- Poor reference standard: most studies use radical prostatectomy (RP), leading to selection bias as those undergoing surgery tend to have burdens of cancer that are distinct from men with an abnormal PSA, and patients choosing other treatments can never be evaluated. Co-registration of an image to an RP specimen is challenging because of shrinkage (10-20%), distortion, tissue loss as a result of 'trimming' (10%), orientation, and absent perfusion.

These deficiencies probably account for the limited acceptance of MRI in contemporary prostate cancer diagnostic pathways.

#### 2.5 Template Prostate Mapping (TPM)

TPM has been selected as the reference test for this study as it meets the required specification for our defined population when using 5mm-sampling (Appendix II: Template Prostate Mapping Protocol, Figure A1):

- TPM produces a histological map of the entire prostate in 3-dimensions.
- TPM has estimated sensitivity and negative predictive value (NPV) in the order of 95% for clinically significant cancers when assessed against radical prostatectomy.
- TPM avoids selection bias since all men exposed to the index test can be exposed to the reference standard.
- TPM has a similar side effect profile to that of TRUS biopsy with 3 important differences:
  - TPM carries a significantly lower risk of urosepsis (<0.5%) the most serious complication of TRUS biopsy - as the needles do not traverse rectal mucosa
  - TPM confers a higher risk of self-limiting failure to void urine (5%) as a result of greater gland swelling compared to 1-2% associated with TRUS biopsy
  - TPM requires a general/spinal anaesthetic

Although the accuracy of TPM is high in the diagnosis of prostate cancer, it is not currently recommended for standard practice since more research is required on its implementation. For more information on TPM Protocol please see Appendix II.

To compare the diagnostic accuracy of MP-MRI (index test) against the TRUS guided biopsy (current standard) both need to be individually compared to TPM (reference standard). Therefore, all patients in the proposed study will undergo all 3 tests (MP-MRI, TPM and TRUS) but the results will be assessed independently by different people. However, it should be noted that the TPM followed by the TRUS will be performed as a combined prostate biopsy (CPB) procedure.

#### 2.6 Definition of clinically significant prostate cancer

MP-MRI (index test) will be assessed against two definitions of clinically significant prostate cancer derived from TPM (reference test). DEFINITION ONE (to be used in measurement of the primary outcomes) and DEFINITION TWO of clinically significant prostate cancer are given in the box below:

DEFINITION ONE (PRIMARY):	Dominant Gleason pattern $\ge 4$ Cancer Core Length $\ge 6$ mm	AND/OR
DEFINITION TWO:	Any Gleason pattern $\geq$ 4 Cancer Core Length $\geq$ 4 mm	AND/OR

#### 2.7 Trial design

The study is a prospective validating paired cohort study. All men in the study will have a MP-MRI, followed by the CPB procedure (TPM followed by TRUS) and each test will be assessed and reported independently from each other (See Trial Schema 1.2). The study will be run in two stages: the pilot phase, followed by the main phase.

The pilot study aims to recruit 50 patients. These will be recruited from two centres (University College London Hospitals (UCLH) NHS Foundation Trust and Basingstoke and North Hampshire NHS Foundation Trust) over one year. It will allow us to:

- Prospectively record the rate of sepsis following the CPB procedure\*.
- Monitor recruitment rate.
- Provide an estimate of the prevalence in the scanned population of prostate cancer according to DEFINITION ONE and DEFINITION TWO.
- Provide estimate of key outcome measures (sensitivity and specificity of MP-MRI compared to TPM, inter/intra-observer reliability of the MP-MRI).
- Provide evidence which, together with data from the literature, will facilitate a preliminary assessment of cost-effectiveness which, in turn, will feed into an assessment of the key design features of the main study.

\* While it is anticipated that the sepsis rate will be low, each event will be reviewed by the TMG and, as appropriate, by the independent Trial Steering Committee (TSC). If deemed necessary for safety reasons, recruitment to the study will be suspended.

Continuation to the main phase will be dependent on the review of the pilot phase by the TSC. The main phase will involve at least six centres recruiting up to 714 men to have the MP-MRI and CPB over an anticipated additional 2 to 3 years. There will be ongoing central safety monitoring and regular review for safety and data quality.

#### 2.8 Translational research

Subject to securing future funding to collect additional blood and urine samples, the following translational objectives will also be addressed in this protocol:

- Clinical validity (sensitivity, specificity, negative and positive predictive values, overall accuracy) of the following biomarkers in the detection of clinically significant prostate cancer:
  - Free/Total PSA
  - o Urinary PCA3
  - TMPRSS-ERG gene fusion
  - o Ultrasound tissue characterisation
- A tissue bank will be established comprising pre and post-DRE urine, serum, plasma and germline DNA for evaluation of future candidate diagnostic markers with respect to TPM findings (tissues collected prior to CPB procedure).

## 3. SELECTION OF CENTRES/CLINICIANS

The study will consist of designated centres (subject to approvals), that have undergone formal training and quality control in conducting and reporting pre-biopsy MP-MRI and the CPB procedure. Centres will be approved by the TMG prior to participation and attendance at training is a pre-requisite for a centre being approved (see section 6.6).

All designated centres should be registered with the MRC CTU. The MRC CTU and the sponsor must receive the following documentation before a centre can be approved to register patients to PROMIS:

- Copy of approval from the centre's Trust R&D department.
- Signed model agreement for non-commercial research in the NHS.
- Full contact details for all site personnel.
- Completed signature list and delegation of responsibilities log. The MRC CTU must be notified immediately of any changes to trial personnel and/or their responsibilities. An up to date copy of this log must be stored in the Trial Master File at the site and also at the MRC CTU. The delegation log will record who is trained to carry out the MP-MRI and biopsy procedures.
- Copies of the most recent version of the patient information sheet (PIS), GP letter and consent form on local headed paper.
- Completed normal ranges form for site.
- Procedure training log, with at least one named responsible person to conduct MP-MRI and CPB.

Once all of this documentation has been received, confirmation of approval to begin recruitment will be sent to the Principal Investigator (PI) at each institution by the trial team at the MRC CTU.

Before a patient is registered, written informed consent must be obtained. The approved PIS and informed consent form are supplied by the MRC CTU and should be presented on local headed paper.

## 4. SELECTION OF PATIENTS

Patients will be considered eligible for registration into this study if they fulfil all of the inclusion criteria and none of the exclusion criteria, as defined below.

#### 4.1 Patient inclusion criteria

1. Men at least 18 years or over at risk of prostate cancer who have been advised to have a prostate biopsy

- 2. Serum PSA  $\leq$  15ng/ml within previous 3 months
- 3. Suspected stage  $\leq$  T2 on rectal examination (organ confined)
- 4. Fit for general/spinal anaesthesia
- 5. Fit to undergo all protocol procedures including a transrectal ultrasound
- 6. Signed informed consent

#### 4.2 Patient exclusion criteria

1. Treated using 5-alpha-reductase inhibitors at time of registration or during the prior 6 months

2. Previous history of prostate biopsy, prostate surgery or treatment for prostate cancer (interventions for benign prostatic hyperplasia/bladder outflow obstruction is acceptable)

3. Evidence of a urinary tract infection or history of acute prostatitis within the last 3 months

4. Contraindication to MRI (e.g. claustrophobia, pacemaker, estimated GFR  $\leq$ 50)

5. Any other medical condition precluding procedures described in the protocol

6. Previous history of hip replacement surgery, metallic hip replacement or extensive pelvic orthopaedic metal work.

Please contact the PROMIS Trial Manager before registering a patient if you have any queries concerning patient eligibility.

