#### 6.2 Visit 3: Combined Prostate Biopsy (TPM + TRUS)

TPM will be performed first under the same general/spinal anaesthetic as the TRUS guided biopsy. The biopsy procedure is combined to reduce patient burden (two visits, two procedures) and also to minimise drop out of patients between biopsies. Biopsies will be taken every 5mm throughout the prostate using a template grid placed over the perineum. Biopsies will be oriented and individually identified to facilitate later correlation of results with imaging.

TRUS guided biopsy of the prostate is to be performed after TPM, under the same general/spinal anaesthetic. This helps ensure results are obtained for the reference test in a biopsy naïve gland that has not undergone swelling and distortion to allow better post-study comparisons of the TPM and MRI findings. It also minimises the risk of infection.

The surgeon performing the CPB procedure will be blind to the MRI results. TRUS guided biopsies will be done in the left lateral position. 10-12 core biopsies will be taken as per national guidelines. Each core will be identified and potted separately. The TPM and TRUS biopsy sets from a particular patient will be sent to different pathologists to minimise bias. The pathologists will independently report results to the MRC CTU on the separate TPM and TRUS electronic CRFs. Please refer to the PROMIS Combined Biopsy SOP.

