#### 6.6 Procedure training, quality control and quality assurance

#### 6.6.1 MP-MRI

All radiologists from non-UCLH centres working on PROMIS will attend UCLH for a minimum of one training day on the conduct and reporting of MP-MRI. Only radiologists attending the training day (or other approved training programme if they cannot attend the training day) will be approved for reporting MP-MRIs within this trial. Quality control (QC) and quality assurance (QA) of the MP-MRI will be outsourced to an independent commercial partner after a process of tender.

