#### Table 2: Data collection timelines

#### 6.8 Blinding

#### 6.8.1 Blinding of MP-MRI results

In order to make sure that the result of the MP-MRI does not influence the conduct of the biopsy, the results of the MP-MRI will not be revealed to either the men having the biopsies nor to the clinicians undertaking the biopsies until after the results of the TRUS guided biopsy and TPM are available (with one exception for unblinding given below). This blinding is necessary to prevent the results of the MP-MRI leading to some change in how the biopsies are conducted and to protect against the possibility that MP-MRI may be made to look either better or worse than it truly is in detecting and/or ruling-out significant cancer. It is essential that

the key reference test (TPM) is done in a truly systematic way so that the MP-MRI prediction can be compared to the appropriate tissue sample. Whilst accepting that TRUS biopsies under general/spinal anaesthetic may be carried out better than standard care (under local anaesthetic), it is also important that the conduct of TRUS guided biopsies is also blind to the MP-MRI so no targeting of suspicious areas occurs.

Radiology reports will be submitted directly and securely to MRC CTU. The CPB procedure will be conducted by someone other than the MRI reporter. Please refer to the PROMIS MRI SOP for more detail.

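### Eligibility does not exclude men with an earlier prostate MRI, so a man sent to biopsy because of an MRI can enter, selected on the index test and outside the blinding safeguards

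*Protocol*

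**What the plan says.** Inclusion criterion 1 in section 4.1 of the protocol is "Men at least 18 years or over at risk of prostate cancer who have been advised to have a prostate biopsy". It does not restrict the reason for the advice.

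Section 4.2 has six exclusions. The second is "Previous history of prostate biopsy, prostate surgery or treatment for prostate cancer", with an allowance for benign outflow procedures. The only one that concerns MRI is the fourth, which begins "Contraindication to MRI (e.g. claustrophobia, pacemaker, estimated GFR" and is about whether a man can be scanned, not whether he has been. Neither the screening and pre-registration steps nor the registration step in section 5 asks about an earlier prostate MRI.

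Section 2.2 describes the men the trial is about. They are judged at risk on PSA, rectal examination, family history or ethnic profile, and "Men undergo prostate biopsy in the absence of accurate imaging that can visualise a suspicious lesion".

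On blinding, section 6.2 says "The surgeon performing the CPB procedure will be blind to the MRI results", and section 6.8.1 says "the results of the MP-MRI will not be revealed to either the men having the biopsies nor to the clinicians undertaking the biopsies" until both biopsy results are available. The mechanism in sections 6.1 and 6.8.1 is that the study MP-MRI report goes to the trials unit and is held there until after the biopsies.

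**The concern.** The trial asks whether MP-MRI should come first, as triage, in men who would otherwise go straight to biopsy. Men already triaged by an MRI do not belong to that population. Where an MRI is done in routine care, men with a clear scan are less likely to be advised to have a biopsy and so less likely to be approached. Men with a suspicious scan are advised to have one and satisfy section 4 as written. For them, entry depends on the test under evaluation.

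The second problem is blinding. Holding back the study report does nothing about an earlier scan in the notes. The man may know its result, and the surgeon may be able to read it. Section 6.8.1 wants no targeting of suspicious areas in the TRUS biopsy, and an older MRI report would make that possible.

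At stake are the specificity and sensitivity of MP-MRI, which support the two primary outcomes in section 9.1.1, and the paired comparison with TRUS.

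**Working it through.** **The plan's own figure.** The eligibility gap has no stated figure attached to it. The target of 714 is checked only to show that it does not depend on the point. With discordant proportions 0.364 and 0.144 (Appendix V, independence row), p = 0.508 and d = 0.22:

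n = (1.960 × √0.508 + 1.2816 × √(0.508 − 0.22²))² / 0.22² = 106.07, rounded up to 107 cases; 107 / 0.15 = 713.3, rounded up to 714.

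This reproduces section 9.2.3.

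**Illustration of the selection effect.**

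Inputs from the protocol: prevalence 15% (section 9.2.1, DEFINITION ONE), specificity 77% and sensitivity 75% (section 9.2.2).

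Assumptions not in the protocol:
- f is the share of entrants who were advised to have a biopsy because an earlier MRI was positive. That MRI is taken to be as accurate as the study MRI. f is not the share with any earlier MRI.
- r is the probability that the study MRI is positive again, taken as equal in men with and without significant cancer.

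Proportion with significant cancer among MRI-selected men: 0.15 × 0.75 / (0.15 × 0.75 + 0.85 × 0.23) = 0.1125 / 0.3080 = 36.5%.

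Apparent sensitivity = [0.1125(1−f) + 0.365 r f] / [0.15(1−f) + 0.365 f]

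Apparent specificity = [0.6545(1−f) + 0.635(1−r) f] / [0.85(1−f) + 0.635 f]

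For f = 10% and r = 1: sensitivity = (0.10125 + 0.0365) / (0.135 + 0.0365) = 80.3%; specificity = 0.58905 / (0.765 + 0.0635) = 71.1%.

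| f | r = 1.0: sens / spec | r = 0.9: sens / spec | r = 0.8: sens / spec |
|---|---|---|---|
| 0% | 75.0 / 77.0 | 75.0 / 77.0 | 75.0 / 77.0 |
| 5% | 77.8 / 74.1 | 76.7 / 74.5 | 75.6 / 74.8 |
| 10% | 80.3 / 71.1 | 78.2 / 71.9 | 76.1 / 72.6 |
| 20% | 84.5 / 64.9 | 80.7 / 66.5 | 76.9 / 68.0 |

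**Against the specificity target.** With 714 men and f = 0 there are about 607 men without significant cancer, and the expected lower 95% limit is 0.77 − 1.96 × √(0.77 × 0.23 / 607) = 73.7%. With f = 10% there are 714 × 0.8285 ≈ 592 such men, and the same formula gives about 67% to 68% for r between 1.0 and 0.9. That is below the 70% target in section 9.2.2.

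**What does not move.** For f = 10% and r = 1, false positives are 0.9 × 0.85 × 0.23 + 0.0635 = 0.2394, so PPV = 0.1378 / (0.1378 + 0.2394) = 36.5%, the value without selection. PPV stays there for every f and r in this model, because r does not depend on disease. NPV stays at 94.6% for r = 1 and is 94.1% for f = 10% and r = 0.9.

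**Dependence on correlated errors.** If the two reads err independently given disease status, the study MRI is positive in 75% of selected men with significant cancer and 23% of those without. Overall repeat positivity is then 0.365 × 0.75 + 0.635 × 0.23 = 42%, and apparent sensitivity and specificity stay at 75% and 77%. The shift therefore needs the second scan to repeat the errors of the first. The rise in sensitivity is the more fragile part: at r = 0.7 and f = 10% it is (0.10125 + 0.7 × 0.0365) / 0.1715 = 73.9%, slightly below 75%.

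**The case against.** The best case on the other side is that few such men would exist. Section 2.2 lists the triggers for biopsy and MRI is not among them. Section 2.4.3 speaks of limited acceptance of MRI in current pathways. The protocol names no centre that scans before biopsy. Section 6.6.1 says only that "All radiologists from non-UCLH centres working on PROMIS will attend UCLH for a minimum of one training day", which shows trial training, not routine pre-biopsy scanning. This stands: the share cannot be derived from the document and was probably expected to be small. A man advised to have a biopsy on PSA alone, whatever an earlier scan showed, also brings no such selection. It does not close the gap, because section 2.2 is background and no criterion enforces it.

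On blinding, section 6.2 asks for a surgeon blind to MRI results without limiting this to the study scan, and section 8.2 makes checks of blinding central to monitoring. Neither gives a procedure for an older report in the notes. The MRI and biopsy SOPs and the registration form are not shown and may address prior scans.

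A reader might go further in four ways, none of which the protocol supports:
- That the biopsy blinding fails as a whole. The gap concerns only men with an earlier scan.
- That TPM cores would be targeted. TPM takes a core every 5 mm throughout the gland (section 6.2, Appendix II), which leaves little room for it. TRUS is the exposed test.
- That PPV is inflated. In the model above it does not change.
- That the comparison with TRUS is biased in a known direction. Selection may raise apparent MRI sensitivity while an open earlier scan may raise TRUS sensitivity, so the net direction is uncertain.

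Nor is it established that the study radiologist sees the earlier MRI. Section 6.1 lets the reporter know clinical details, and section 9.3.3 explains these as PSA and DRE findings.

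**Conclusion.** The gap is real and can be read directly from section 4: a man advised to have a biopsy because of a suspicious MRI is eligible. He falls outside the population described in section 2.2, he enters by virtue of the index test, and the safeguards in sections 6.1 and 6.8.1 do not reach his earlier scan.

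The size of the effect is conditional. With 10% of entrants MRI-selected and 90-100% repeat positivity, specificity would read about 71-72% instead of 77% and sensitivity about 78-80% instead of 75%. At 5% the specificity shift is about 2.5 to 3 points. With independent errors it is zero. These figures illustrate direction and scale and do not predict that the trial would miss its specificity target. The point is worth acting on because the remedy is cheap and is best applied at entry. On the same 10% assumption, removing these men only at analysis would leave 0.9 × 0.15 × 714 ≈ 96 cases, below the 107 planned for the paired comparison.

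**What to change.** In section 4.2, add *previous MRI of the prostate* to exclusion criterion 2. At minimum, exclude men whose biopsy was advised on the basis of, or with knowledge of, a prostate MRI.

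For men already registered, establish whether each had a prostate MRI before entry, and repeat the primary accuracy measures without those who did. If the registration form does not already record this, one yes/no item is enough.

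The cost is one line in the criteria, at most one item on a form, and a few candidates lost at any centre that already scans before biopsy. The sample size calculations and the target of 714 men with all three tests stay as they are.
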